7.1.2 Hugo™ RAS Arm Cart Assembly

The arm carts consist of movable platforms with casters, each supporting a modular and extendable arm. Up to four arm carts can be connected to the system tower for simultaneous use during RAS. The arm carts are portable and easily movable within the operating room and the hospital. Prior to surgery, the OR team positions the arm carts around the surgical table according to the surgical procedure. The team can adjust the arm carts and arms to accommodate subject positioning and optimize bedside access to the subject.

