10.6 Assessment of Safety

Safety will be evaluated through the study primary endpoint (major complications) and several secondary endpoints (**Section 5.1.4**).

Safety will also be assessed by monitoring the occurrence of adverse events (AEs), serious adverse events (SAEs), deaths, adverse device effects (ADE), serious adverse device effects (SADE), unanticipated adverse device effects (UADE) or device deficiencies. Adverse event assessments will take place starting with the point of consent, through the end of study exit through 5-year follow-up, or until resolution whichever comes first and will be recorded in the eCRF.

Medtronic Business Restricted

This document is electronically controlled

CONFIDENTIAL 056-F275 Rev E Clinical Investigation Plan Template

AEs will be collected from the time of consent. AEs occurring in subjects excluded from the full analysis set (FAS) (**Section 14.1**) will be followed post-consent through study exit and will be reported in a listing in the clinical study report (CSR).

These AEs will not be included in the FAS summary analysis for either AE reporting or the analysis of the primary and secondary endpoints.

For the FAS, the type, incidence, severity, duration, and procedure/device relatedness of AEs will be reported. AEs for all FAS subjects will be analyzed from first incision through the study exit.

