12.1 Adverse Events

All Adverse Events (AEs) will be collected, starting from the time the informed consent form is signed through 30 days (+7) after the day of the procedure regardless of their severity or relationship to the Hugo™ RAS or study procedures. After 30 days, AEs will be assessed by the surgeon and those AEs deemed attributable to the underlying surgical indication, procedure or surgical device will be reported. All deaths will be collected via AE regardless of relatedness. Reporting of these events to Medtronic will occur on an AE Form, including event description, date of AE, treatment, resolution, assessment of both the seriousness of the AE and the relatedness to the system components. Each AE must be recorded on a separate AE eCRF.

AE definitions used in this study are based on ISO 14155:2020 (Clinical Investigation of Medical Devices for Human Subjects -- Good Clinical Practice). Documented pre-existing conditions are not considered AEs unless the nature or severity of the condition has worsened. See **Section 14.1** for details regarding AE analyses in each study analysis set. In addition, AEs impacting users or other persons (non-subject AEs) will be collected on a non-subject AE CRF.

Any unresolved procedural or device-related events that are still ongoing past study exit will be monitored by the physician per their institutional standard-of-care.

Unavoidable adverse events (UAE) (those that are inherent to the procedure and are expected to occur in all subjects for an expected duration) listed in **Table 9** will not be captured or reported unless the adverse event worsens or persists outside the stated timeframe post procedure. **Section 11.1** includes a list of several, but not an all-encompassing anticipated adverse events.

All deaths, serious adverse events related to the Hugo™ RAS System and/or study procedures and Clavien-Dindo Grade III and IV complications will be adjudicated by an independent CEC.

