14.9 Analysis Populations

The following populations will be considered for the analysis of data for this study:

Full Analysis Set

The full analysis set (FAS) is defined as all enrolled subjects in whom the Hugo™ RAS procedure is begun, defined as the first skin incision. This is also known as a modified intent-to-treat (mITT) population. In the event that a subject is consented, but the first incision does not occur (e.g., if the subject becomes ineligible during the timeframe between consent and the procedure day), that subject will not be considered part of the FAS. The FAS will be the primary analysis set for the evaluation of the primary and secondary endpoints.

AEs will be collected from the time of consent. AEs occurring in subjects excluded from the FAS will be followed for 30 days post-consent through study exit and will be reported in a listing in the clinical study report. These AEs will not be included in the primary FAS analysis for either AE reporting or the analysis of the primary and secondary endpoints. The number and proportion of subjects experiencing each type of adverse event will be summarized by site and overall for the FAS.

Per Protocol Analysis Set

The per protocol analysis set (PPAS) is a subset of the FAS including only those subjects without any major protocol deviations. Prior to data analysis, a protocol deviation listing will be produced and sent to the clinical manager/team for review in order to verify which subjects will be excluded from the PPAS. Reasons for exclusion of subjects from PPAS will be documented and reported.

All enrolled subjects will be included in a subject disposition table indicating reasons for exclusion from the FAS and PPAS analysis sets.

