7.10 Safety Evaluation

In addition to the primary and secondary safety endpoints, other safety measures will be assessed for the FAS population as well. These include data of adverse events and device deficiencies (DD).

Adverse Event definitions used in this study are based on ISO 14155:2020 (Clinical Investigation of Medical Devices for Human Subjects -- Good Clinical Practice). DD is defined as any inadequacy of a medical device with respect to its identity, quality, durability, reliability, usability, safety, or performance. This includes malfunctions, use errors, and inadequacy in the information supplied by the manufacturer such as labeling.

For a summary of adverse events (AEs), the frequencies of adverse device effects (ADEs), serious adverse events (SAEs), serious adverse device effects (SADEs) and unanticipated adverse device effects (UADEs) will be presented in the CSR in tabular format as well as listings. AEs relatedness will be summarized and presented. For AEs related to procedure and the investigational device Hugo™ system, a detailed summary will be presented by MedDRA preferred term and system organ class (SOC).

DDs will be presented in summary tables displaying the number of deficiencies, and the number and percentage of subjects with deficiencies.

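### In treated subjects, AEs that start between consent and first incision fall in neither of the protocol's two AE outputs, and the SAP does not settle the window

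*Protocol*

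**What the plan says.** **Collection.** Protocol 10.6 starts AE collection at consent ("AEs will be collected from the time of consent"). Section 12.1 agrees: "starting from the time the informed consent form is signed through 30 days (+7) after the day of the procedure".

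**Outputs.** Protocol 10.6 and the Safety Assessments row of the synopsis name two. For FAS subjects, "AEs for all FAS subjects will be analyzed from first incision through the study exit". For consented subjects who are never incised there is a listing, restated in 14.9: "AEs occurring in subjects excluded from the FAS will be followed for 30 days post-consent through study exit and will be reported in a listing". Section 14.9 also promises a summary of AE types for the FAS and gives it no start time.

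**What happens before incision.** Protocol 10.1.1 allows screening and consent up to 30 days before the procedure. Section 10.1.2 puts subject positioning, by the anesthesia and surgical teams, ahead of the first incision. Section 7.1.2 adds: "Prior to surgery, the OR team positions the arm carts around the surgical table according to the surgical procedure".

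**Deficiencies.** Protocol 12.2 directs that a device deficiency resulting in an AE to the subject is recorded as an AE and not also as a deficiency.

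**SAP.** Section 7.10 says that "other safety measures will be assessed for the FAS population as well" and plans tables and listings of ADEs, SAEs, SADEs and UADEs, with no start point. The major-complication derivation in 7.9.2.2, and most of the AE-based derivations in 7.9.3.1, set only an upper limit of 30 calendar days after the procedure.

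**The concern.** The interval from consent to incision includes the first point at which the investigational system is placed around the subject. Protocol 11.1 lists crushing injury, blunt trauma and electric shock among the system's hazards, without saying when in the procedure they would arise. Protocol 11.5 classes the system as significant risk, and the study is pivotal.

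If the 10.6 sentence is followed literally, a device-related injury with onset during set-up in a subject who is then treated would be absent from the protocol's aggregate AE analysis and from its listing. The aggregate account in the study report is what a reader uses to judge device-related harm, and individual reports sent during the study do not replace it. If the SAP is read without a start point, the same event would be included. Two programmers could therefore build different AE tables from the same data.

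**Working it through.** No power or alpha figure is involved. The check is to trace cases through the stated rules.

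1. **Set-up injury before incision, operation goes ahead.** The subject is in the FAS.
   - Recorded on the eCRF: yes (10.6, 12.1).
   - Reported individually according to type: yes (12.5, Table 10).
   - In the protocol's FAS AE analysis: no (10.6 starts at incision).
   - In the protocol's listing: no (non-FAS subjects only).
   - In the primary safety endpoint as worded: no (first incision onward; Protocol 5.1.3, SAP 4.1.2 and 7.9.2).
   - In the SAP 7.10 tables and listings: not excluded, but not settled.
2. **Same injury, operation cancelled before incision.** The subject is outside the FAS, so the event is listed. The injury is handled differently depending only on whether surgery followed.
3. **Pre-procedure malfunction without harm.** SAP 7.9.3.1, endpoint 10, counts deficiencies before, during or after the procedure, so it is counted.
4. **Pre-incision malfunction that injures the subject.** Under Protocol 12.2 it is recorded only as an AE, so it can leave the deficiency count. Its onset is before incision, so it is also outside the FAS AE analysis in 10.6. The harmless malfunction in case 3 is counted, while the harmful one may not be.
5. **Derivations.** SAP 7.9.2.2 and, in 7.9.3.1, overall complications, transfusion and reoperation have an upper limit only. Readmission, 30-day mortality and overall survival do carry a lower limit. SAP 4.1.2, 4.2 and 7.9.2 say that the complication endpoints start at first incision, but the derivations do not apply that limit.
6. **Can the boundary be applied to the data?** The AE form holds the date of the event (Protocol 12.1), and SAP 7.9.2.2 compares AE start date with procedure date. The time of first incision is available, since SAP 7.9.3.1 uses it for operative time, but neither document mentions a time of AE onset. On the day of surgery, dates alone cannot separate before from after.

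**Illustration only.** The documents give no rate. Suppose that 0.5% to 1% of treated subjects have a pre-incision AE that matters, and take the maximum of 141 subjects. The chance of at least one is 1 − 0.995^141 = 0.507 to 1 − 0.99^141 = 0.758. This restates the assumed rate; it is not evidence about this device, and it does not show that such an event would be left out.

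**The case against.** A reader might infer that set-up harms escape the study's safety reporting altogether. The documents do not support that. These AEs are recorded from consent. SAEs, ADEs, SADEs and UADEs follow the Table 10 routes with no first-incision limit. Deaths, related SAEs and Grade III and IV complications go to the independent events committee (12.1).

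A reader might also infer that the protocol and SAP produce different AE counts. That rests on the SAP's silence. The SAP says that it elaborates on the protocol, so it may inherit the first-incision start; alternatively, its FAS tables and listings may have no lower limit and so include these events. Either reading is possible, and the supportable statement is that the window is unsettled.

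Three further points stand:

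- Analyzing from a given time does not forbid listing earlier events, and the sentence before the quoted one in 10.6 has no start time.
- With date-level data, a set-up injury on the day of surgery might be counted with post-incision events. The AEs that dates would clearly exclude are those on earlier days, before device exposure.
- A first-incision start is a sensible match to the FAS definition and to the endpoint window, and an injury with onset after incision is counted.

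These points limit the consequence, but they do not give the pre-incision AE of a treated subject a stated place in the report. They also show that the outcome currently depends on programming choices.

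**Conclusion.** The point holds as a gap in the planned aggregate AE account and in the agreement between the two documents. It does not show that harms go uncollected or unreported. Read literally, the protocol leaves AEs with onset between consent and first incision in FAS subjects out of both its FAS analysis and its listing, and the SAP does not say whether its own tables include them. The interaction with 12.2 is the most consequential part, because a malfunction that causes harm can be less visible in the summaries than one that does not.

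The primary safety endpoint as worded is unaffected, since it starts at first incision, but the SAP 7.9.2.2 derivation lacks that lower limit and should be corrected. The number of events at issue cannot be estimated from the documents and may be zero. The conclusion rests on reading 10.6 as written and on the absence of any stated AE onset time. It is a minor, inexpensive correction.

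**What to change.** - Keep the endpoint analyses from first incision, and write that lower limit into SAP 7.9.2.2 and the overall-complication derivation in SAP 7.9.3.1.
- In Protocol 10.6, the synopsis, Protocol 14.9 and SAP 7.10, add a separate count and by-subject listing of AEs from consent to first incision in FAS subjects, with seriousness and device and procedure relatedness.
- State that the ADE, SADE and UADE totals include device-related events from system set-up onward, so that those totals have one defined window even though the general FAS AE tables start at incision.
- Flag each AE on the day of surgery as before or after first incision.

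The cost is a few sentences, one extra listing and one flag. Apart from the flag, the data are already collected. Sample size, power and alpha do not change.

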10.7 Recording Data

Data entered must be traceable to source documents. Source documentation is defined as the first-time data appear, and may include original documents, data, and records (e.g., hospital records, clinical and office charts, procedure reports, laboratory notes).

In general, eCRFs (or paper copies) may not serve as source documents. Source documentation for data elements not routinely captured in medical records may vary from study site to study site; the study site may use source document worksheets if identified as source documents.

The Investigator must ensure the availability of source documents from which the information on the eCRFs was derived. The type and location of source documents should be documented. Where printouts of electronic medical records, are provided as source documents, or where copies of source documents are retained as source documents, those should be certified. Certification must contain (1) the signature of the individual making the copy and (2) the date the copy was made.

The source documents must be made available for monitoring or auditing by Medtronic's representative or representatives of the competent authorities and other applicable regulatory agencies.

The CRF may be considered source for the following data collection elements:

- Enrollment Notification
 - Study site assigned subject reference
- Baseline
 - Administrative information
- AE eCRF
 - Date study site became aware of event
 - Relatedness of adverse event
- DD eCRF
 - Date study site became aware of event

- Subject Death
 - Date study site became aware of death
 - Relatedness of death
- Deviations
 - Reason for deviation

10.8 Deviation Handling

A study deviation is defined as an event within a study that did not occur according to the CIP or the CTA.

Prior approval by Medtronic is expected in situations where the Investigator anticipates, contemplates, or makes a conscious decision to deviate. Prior approval is not required when a deviation is necessary to protect the safety, rights, or well-being of a subject in an emergency or in unforeseen situations beyond the Investigator's control (e.g., subject failure to attend scheduled follow-up visits, inadvertent loss of data due to computer malfunction, inability to perform required procedures due to subject illness).

For medically justifiable conditions which preempt a subject's ability to complete a study-required procedure, it may be permitted to report only one deviation which will apply to all visits going forward. This may also apply for other unforeseen situations (e.g., the subject permanently refuses to complete a study required procedure and the data will not contribute to the primary end point analysis). However, prior approval from Medtronic is required for such situations.

All study deviations must be reported on the CRF regardless of whether medically justifiable, pre-approved by Medtronic, an inadvertent occurrence, or taken to protect the subject in an emergency. Multiple deviations of the same type at the same visit may be reported on one case report form.

In the event the deviation involves a failure to obtain a subject's consent or is made to protect the life or physical well-being of a subject in an emergency, the deviation must be reported to the IRB as well as Medtronic within five (5) working days. Reporting of all other study deviations should comply with IRB policies and/or local laws and must be reported to Medtronic as soon as possible upon the study site becoming aware of the deviation. Reporting of deviations must comply with IRB policies, local laws, and/or RA requirements.

Medtronic is responsible for analyzing deviations, assessing their significance, and identifying any additional corrective and/or preventive actions (e.g., amend the CIP, conduct additional training, terminate the investigation). Repetitive or serious Investigator compliance issues may result in initiation of a corrective action plan with the Investigator and study site, and in some cases, may necessitate suspending enrollment until the problem is resolved or ultimately terminating the Investigator's participation in the study. Medtronic will provide study site-specific reports to Investigators summarizing information on deviations that occurred at the investigational study site on a periodic basis.

If during the procedure, the Investigator changes from HUGO™ to another RAS system (even if it is in conjunction with HUGO™), it will no longer be a protocol deviation, but it will be captured as a device deficiency as needed/applicable. If the Investigator converts to laparoscopic or open surgery, it will not be considered a protocol deviation.

Examples of study deviations include but are not limited to:

- Failure to obtain proper IC
- Failure to collect required study data
- Inclusion/exclusion criteria not met

10.9 Subject Exit, Withdrawal or Discontinuation

Subjects may voluntarily withdraw from the study at any time. Additionally, the Principal Investigators may withdraw or choose not to enroll subjects if they feel they do not meet the CIP defined inclusion and exclusion criteria or if it is in the best medical interest of the subject in question. If the study Investigator voluntarily removes a subject from further study participation, supporting documentation must be in place for the rationale and date of removal.

Every attempt will be made to contact subjects who are noncompliant. Subjects will be considered lost to follow-up once the following steps have been taken:

- Three phone calls should be made to the subject. Each attempt should be clearly documented in the source documents and the response or lack thereof should be captured.
- If there is no response to the phone calls, then a certified/registered letter should be written to the subject. A copy of the letter should be retained in the subject's source document.
- After a period of two weeks following completion of the above actions, the subject will be considered lost to follow-up. The sponsor should be notified and the Study Exit form should be completed.

In cases of early study exits, all data collected from the time of informed consent to the time of exit may be used. Subjects who exited early will not be replaced. Enrollment will continue as per CIP definitions up to the predefined maximum number of subjects.

The reason and date for study exit of all enrolled subjects will be documented on the applicable electronic case report form (eCRF).

All subjects will be followed per institutional standard of care after any withdrawal, discontinuation, or completion of the study follow-ups.

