10.1.5 Post-Operative Follow-Up Visits (Visit 4-8)

Post-operative visits 4-8 for oncologic subjects will be made via a phone call to assess overall survival, progression-free survival, and disease-free survival.

Medtronic Expand URO Clinical Investigation Plan

MDT19051EINURO

Version 9.0

Page 40 of 111

Medtronic

Table 6. Data Collection and Study Procedure Requirements at Subject Visits

Procedure/Assessment	Screening (Day -30 to 0) Visit 1	Surgical Procedure (Day 0) Visit 2	Hospital Discharge Visit 2.1	Follow-Up (30+7 Days) Visit 3	Follow-up (Years 1 - 5) (+/- 3 mo. window) Visits 4-8
	May be Combined				
Informed Consent Form ¹	X	X			
Eligibility Criteria	X	X			
Demographic Data	X				
Medical/Surgical History	X				
Concomitant Medication(s)	X	X	X	X	
Lab Values (if applicable)	X	X	X	X	
Robot Setup Time		X			
Total Operative Time (skin to skin)		X			
Surgeon Console Time		X			
Instruments Used		X			
Estimated Blood Loss		X			
Transfusion ³		X	X	X	
Conversion to a robotic-assisted approach utilizing an FDA cleared robotic-assisted device, open or manual laparoscopy		X			
Robot Take Down Time		X			
Warm Ischemia Time (if applicable)		X			
Anastomotic Leak Test performed (if applicable)		X			
Anastomotic Stricture (if applicable)		X			
Rate of Positive Circumferential Margins on Final Pathology (if applicable)		X			
Margin (mm) (if applicable)			X		

Medtronic Business Restricted

This document is electronically controlled

CONFIDENTIAL 056-F275 Rev E Clinical Investigation Plan Template

Medtronic Expand URO Clinical Investigation Plan

MDT19051EINURO

Version 9.0

Page 41 of 111

Medtronic

Procedure/Assessment	Screening (Day -30 to 0) Visit 1	Surgical Procedure (Day 0) Visit 2	Hospital Discharge Visit 2.1	Follow-Up (30+7 Days) Visit 3	Follow-up (Years 1 - 5) (+/- 3 mo. window) Visits 4-8
Tumor Size (if applicable)			X		
Tumor Stage (if applicable)			X		
Total number of lymph nodes retrieved			X		
Catheterization Time			X	X	
Mortality			X	X	X
Length of Hospital Stay			X		
Reoperation			X	X	X
Pain Medication			X	X	
Medications if associated with an AE	X	X	X	X	X
Adverse Events ²	X	X	X	X	X
Readmission				X	X
Device Accountability		X			
Device Deficiency		X			
Protocol Deviation Collection (if applicable)	X	X	X	X	X
Study Exit				X	X

¹Study specific procedures may only be performed after subject has agreed to participate and signed the informed consent form.

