10.9.1 Study Exit

A study exit eCRF is required for all subjects. Prior to exiting a subject from the study, it is recommended

to follow the subject until all ongoing system and/or procedure related AEs are resolved or unresolved with no further actions planned.

Following exit, subjects will continue to receive standard medical care. Upon exiting from the study, no further study data will be collected, or study visits will occur for the subject. All data available through the time of the subject's exit will be used for analysis.

Subjects are urged to remain in the study as long as possible but may be exited from the study for any of the following situations:

- Study completed
- Subject lost to follow-up
- Subject death
- Subject did not meet inclusion/exclusion criteria
- Subject did not provide consent (or data use protection authorization)
- Subject chooses to withdraw (e.g., consent withdrawal, relocation to another geographic location)
- Investigator deems withdrawal necessary (e.g., medically justified, inclusion/exclusion criteria not met, failure of subject to maintain adequate study compliance)

The following information is required to be collected at study exit:

- Reason for exit

If discontinuation is because of safety or lack of effectiveness, the subject shall be asked to be followed for collecting safety data outside the clinical investigation.

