7.9.3.5 Analysis Methods

Secondary objectives 1, 4, 5, 7, 8, 9 and 10 will be summarized by surgery as the count and proportion of subjects experiencing the given endpoint, with a 95% confidence interval.

Secondary objectives 2, 3 and 6 will be summarized by surgery performed using mean, standard deviations (SD), median, IQR, and range. A 95% confidence interval will also be calculated.

Secondary objectives 11, 12 and 13 will be evaluated through separate Kaplan-Meier analyses by surgery.² The event for each Kaplan-Meier will be their respective objective endpoint. Subjects will be censored upon study completion (5-year follow-up visit) or they are lost to follow-up without event. For subjects that are lost to follow-up, their last visit date or date of last subject contact will be used as their censor date, whichever occurred later. The 5-year survival will be estimated from the Kaplan-Meier model and a 95% confidence interval will be calculated.

Secondary objective 1 will have three additional exploratory analyses wherein the overall complication rate within 30 days will be limited to each of: related to device, related to procedure, and related to underlying condition. Relatedness in this exploratory analysis will be any rating other than “Not Related” or equivalent.

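### One failed contact round ends scheduled follow-up for oncologic subjects, with no retry at later yearly calls, so recoverable 5-year progression and recurrence data are given up

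*Protocol*

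**What the plan says.** Protocol 10.9 gives one contact sequence for all subjects. "Three phone calls should be made to the subject". "If there is no response to the phone calls, then a certified/registered letter should be written to the subject". "After a period of two weeks following completion of the above actions, the subject will be considered lost to follow-up". The site's next step is "The sponsor should be notified and the Study Exit form should be completed". Section 10.9.3 defines loss to follow-up by pointing back to these conditions. Section 10.9.1 states the effect of exit: "Upon exiting from the study, no further study data will be collected, or study visits will occur for the subject".

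The long-term schedule is in Protocol 10.1.5: "Post-operative visits 4-8 for oncologic subjects will be made via a phone call to assess overall survival, progression-free survival, and disease-free survival". Table 6 places these contacts at years 1 to 5, each with a window of 3 months either side.

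Several passages soften the rule. The list of exit reasons in 10.9.1 opens permissively: "Subjects are urged to remain in the study as long as possible but may be exited from the study for any of the following situations". Section 10.9.3 asks the investigator to try to confirm whether a lost subject is alive. Section 12.3 asks for continued follow-up of unresolved system- or procedure-related adverse events after an early exit. Section 10.9.6 ranks reduced data collection above exit.

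For the long-term analysis, SAP 7.9.3.5 says: "Subjects will be censored upon study completion (5-year follow-up visit) or they are lost to follow-up without event". The censoring date is the later of the last visit and the last contact with the subject.

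**The concern.** The sequence in 10.9 suits a study that ends at day 30, where a subject who cannot be reached has little follow-up left to lose. For oncologic subjects it also governs a series of yearly phone calls. Someone who cannot be reached around year 1 may well answer at year 2, but once the exit form is completed, the text provides for no further scheduled call and no way back in. An oncologic subject who cannot be reached for the 30-day visit falls under the same rule.

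At stake are the 5-year secondary endpoints, above all progression-free and disease-free survival. Both depend on the site recording disease status during follow-up (SAP 7.9.3.1), and early exits are not replaced (Protocol 10.9). Kaplan-Meier estimation treats loss as unrelated to outcome. If subjects who cannot be reached differ in prognosis from those who can, censoring them at the last contact may be informative.

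**Working it through.** **Step 1: the trigger.** Under Protocol 10.9 a complete round must fail: three calls, the letter, and two further weeks. One such round is enough. Neither 10.9 nor 10.9.3 requires a second missed visit, sets a separate rule for the yearly oncologic contacts, or describes re-entry.

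**Step 2: what continues after exit.**

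| Item | Source | After exit for loss |
|---|---|---|
| Scheduled yearly contacts | 10.9.1 | Stop |
| Disease status | 10.9.1; SAP 7.9.3.1 | Stops |
| Vital status | 10.9.3 | Efforts made; frequency not stated |
| Unresolved system- or procedure-related adverse events | 12.3 | Efforts to continue |

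The last two rows conflict with the flat bar on data in 10.9.1 and need to be reconciled with it.

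**Step 3: effect by endpoint.** SAP 7.9.3.1 counts a death for overall survival if it is recorded as an adverse event leading to death, or if the site notes it during follow-up. A death found through vital-status efforts could therefore still enter. Overall survival is partly protected, although the SAP does not say how a vital-status result obtained after loss affects the censoring date. Death is also an event for progression-free and disease-free survival, so what those endpoints lose is non-fatal progression and recurrence.

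**Step 4: size, as illustration only.** The documents state no 5-year retention or yearly loss rate, so there is no plan figure to reproduce. The only attrition allowance is the 10% used to size the primary endpoints (Protocol 14.4 and 14.7), and it does not address 5-year loss. Let q be the assumed chance that a full round fails in a given year, independent across years, with deaths ignored.

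- Present rule: share out of follow-up by year 5 = 1 − (1 − q)^5
- Yearly retries: share not reached at year 5 = q

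| q | Present rule | Yearly retries |
|---|---|---|
| 2% | 1 − 0.98^5 = 9.6% | 2% |
| 5% | 1 − 0.95^5 = 22.6% | 5% |
| 10% | 1 − 0.90^5 = 41.0% | 10% |

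If all 31 cystectomy subjects were oncologic and q were 5%, about 31 × 0.774 = 24 would still be followed at year 5 under the present rule, against about 31 × 0.95 = 29 reached with retries.

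**Step 5: sensitivity to the assumptions.**
- Independence drives the contrast. If the same people fail every round, the share lost is q under either rule and the gap is zero. The truth probably lies between these extremes.
- Deaths reduce the absolute counts. With the mean 5-year cystectomy survival of 0.645 in Protocol 14.5, about 31 × 0.355 = 11 of 31 would die before year 5, so not all 31 are at risk of loss throughout.
- Subjects who exit still contribute time up to censoring.

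**The case against.** The strongest reply is that the protocol treats exit as a last resort. Section 10.9.1 says subjects may be exited, 10.9.6 prefers reduced data collection, and 10.8 gives failure to attend a follow-up visit as an example of an unforeseen deviation, so a missed-visit category exists. These show intent, but none overrides 10.9 for a subject who cannot be reached. There, the status after two weeks is stated without condition and the form is to be completed. Section 10.9.6 covers a subject who chooses to disengage or an investigator who deems it necessary; it does not name unreachable subjects.

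Four stronger readings are tempting, and the documents do not support them.

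- A reader might infer that one unanswered yearly call removes a subject. It does not; the whole round must fail.
- A reader might infer that all data collection then ends. Sections 10.9.3 and 12.3 keep vital-status efforts and follow-up of related adverse events.
- A reader might infer that sites will exit subjects before the annual window closes. The contact steps are for noncompliant subjects, and no passage tells sites to run them early. The text simply does not tie them to the window.
- A reader might infer that the censoring flatters the device. Subjects who cannot be reached may be sicker, which is plausible, but nothing in the documents establishes the direction.

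It is also fair to say that people who ignore three calls and registered mail have often moved or disengaged, in which case retries recover little.

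**Conclusion.** The concern holds in a limited form. Read as written, 10.9 and 10.9.1 end scheduled follow-up of an oncologic subject after one complete failed contact round, with no rule for later annual windows or for re-entry. Disease-status data for 5-year progression-free and disease-free survival are given up although a later call might recover them. Overall survival is partly protected. Censoring at loss may be informative, in a direction that the documents do not settle.

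The size is unknown. The percentages in the working rest on an assumed failure rate, independence between years and no deaths; they show how the rule compounds and are not a forecast. The affected endpoints are descriptive and unpowered, with performance goals used as benchmarks (Protocol 14.5, SAP 7.9.3). The 30-day primary endpoints, and study success as Protocol 14.1 defines it, are not affected. This is an inexpensive improvement worth making, not a flaw in the main analysis.

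**What to change.** Amend Protocol 10.9, 10.9.1 and 10.9.3 for oncologic subjects who have not withdrawn consent:

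- Record a failed contact round as a missed visit, not a study exit.
- Repeat the round in each later annual window.
- Complete the Study Exit form for loss to follow-up only after the year-5 window closes without contact.
- If the subject is reached again, resume follow-up and record interval disease status with dates.
- Reconcile the bar on data in 10.9.1 with 10.9.3 and 12.3, and state how often vital status is sought.

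Keep the present rule for non-oncologic subjects. In the SAP, say how vital status obtained after a contact gap enters the overall-survival censoring rule, and flag progression or recurrence first learned of after such a gap, because its date is known only to an interval.

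A milder alternative is to require two consecutive failed rounds before exit. Under the same assumptions it would lose about 0.2%, 1.0% or 3.7% by year 5 for q of 2%, 5% or 10%.

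The cost is protocol and SAP wording, a few extra calls per unreachable subject each year, and some interval-dated events to handle in the analysis. No new visit or procedure is needed. The consent form is under separate cover and should be checked to see that it allows the repeated contact.
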